## 7. STATISTICAL CONSIDERATIONS

### 7.1. SAMPLE SIZE

The primary endpoint of the study is to replicate the diagnostic performance of the VIDAS TBI assay to predict whether the tested patient would be positive or negative from brain injury visible on head CT scan and to determine that implementation of the VIDAS TBI, in the standard of care of patients with mTBI, is not associated with serious side effects during the six-month period of the study. We expect to test during a six-month period around 1000 patients (from the 3500 patients with suspected TBI that are admitted to our hospital yearly approximately (data from discharge diagnosis of patients with TBI related diagnostic codes)). With this sample size and with an expected prevalence of 10% of CT positivity we expect to have at least 100 patients with positive CTs. With this sample size we expect to replicate the NPV of the BRAINI study with an expected lower bound of the 2-sided 95% CI greater than or equal to 97.0%.

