1. STUDY SUMMARY

TITLE	Blood Biomarkers to improve management of mild traumatic BRAIN Injury implementation study
RUNNING TITTLE	BRAINI2 Implementation study
GENERAL OBJECTIVE	To assess the applicability and added value of a new clinical management pathway for patients with mild TBI presenting to the emergency department (ER), including the use of an in vitro diagnostic assay measuring the biomarkers GFAP and UCH-L1 in the serum, within the first 12 hours post-injury, to rule out the need for CT scan in mild TBI patients.
PRINCIPAL OBJECTIVE	
 
1) To evaluate the diagnostic performance of the VIDAS TBI (GFAP&UCH-L1) test in determining the need for CT-scan in patients with mild TBI admitted to the ER of Hospital 12 de Octubre.
 
2) To determine the safety of a management protocol including the use of the VIDAS GFAP&UCH-L1 test for patients with mTBI, in terms of complications or unforeseen neurological deterioration following the injury.
 
3) To estimate the reduction of CTs achieved using the biomarker test, by comparison with the management of TBI during the six months preceding the study (reference pathway).
 

PRINCIPAL OUTCOME	
Abnormal CT scan at admission in the ER
 
Deterioration: need for hospital admission or surgery due to TBI in the first week after TBI
 
Number of CTs prescribed in the management of mild TBI patients in the ER

PRINCIPAL OUTCOME MEASURES	
 
1) Diagnostic performance of the biomarker test
 
2) Proportion (%) of neurologic deterioration within 1 week post-TBI
 
3) Proportion (%) of CT scan prescribed in the ER over the period of the study for patients with mTBI
 

SECONDARY OBJECTIVES	
 
2.1) To determine the different times involved in the management of mild TBI patients and the effect of using the combined VIDAS test.
 
2.2) To establish differences in direct costs in the management of mild TBI in Hospital 12 de Octubre.
 
2.3.) To assess the compliance of physicians to the proposed algorithm.
 

SECONDARY OUTCOMES	
 
2.1) Time from admission to discharge. Time from admission to sample obtention. Time from venipuncture to availability of biomarker results.
 
2.2) Directs costs associated with mTBI management in the ER.
 
2.3.) Compliance with proposed algorithm.
 

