## BRAINI2-IMPLEMENTATION STUDY

Patients with mTBI lesions are often hospitalised in the standard ward where neurological monitoring consists of repeated CT scanning and clinical exams. Patients without lesions on the initial head CT-scan are also hospitalised when their GCS score after CT scan is less than 15.

Additionally, elderly patients on anticoagulants or antithrombotic drugs are more frequently hospitalised due to physicians' concerns about potential deterioration. This determines a bigger number of unneeded hospitalisations for these patients.

Therefore, although CT scan plays a pivotal role in the management of mTBI, there is an unmet clinical need for an objective tool to optimize and guide indications for CT scan, reduce clinical practice variability, reduce patient radiation exposure and improve patient outcome prediction.

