## BRAINII2-IMPLEMENTATION STUDY

positive (beyond the threshold concentration). This test has been already tested in a large number of European patients and has presented good safety and reliability profiles.

To determine the safety of the new protocol all information regarding the neurological status of the patients in relation to mTBI will be analyzed up to two weeks after the mTBI, specifically neurological deterioration, need for further observation of the patient or admission or need for treatment(medical or surgical) related to mTBI.

In order to determine the reduction of CT scans obtained with this new protocol, absolute numbers and proportions of patients finally scanned using this new protocol will be compared to the reference management of a similar number of patients during a similar historical period(i.e. data from the previous six month for patients attended for mTBI at Hospital 12 de Octubre).

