### 5.3. PARAMETER ASSESSMENTS

#### 5.3.1. Clinical parameters

1) Vital signs will be measured in the emergency department according to standard practice (GSC score, arterial blood pressure, heart rate, respiratory rate, body temperature, pulse oximetry). The presence of vomiting, nausea or headache will be recorded, as well as the presence of loss of consciousness. All recorded variables will be obtained following the standard of care of the workup of the mTBI patient established in the Hospital and no extra information will be obtained.

Secondary deterioration within the first week after TBI will be obtained by reviewing electronic medical history of the patient's and new contacts during this week with the ER, and is defined as follows:

- a decrease in GCS score of more than 2 points from the initial GCS score in the absence of sedatives
- a deterioration in neurologic status sufficient to warrant intervention, i.e. mechanical ventilation, sedation, osmotherapy, neurosurgical procedure or admission to the intensive care unit.
- Admission to a hospital ward exclusively related to deterioration of neurological condition due to TBI.

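### Section 7.1 promises to establish that the pathway is safe, but the one safety measure has no bound, is defined in two ways, and is not tied to the patients left unscanned after a negative test

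*Protocol*

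**What the plan says.** Safety is the second principal objective in the study summary: "To determine the safety of a management protocol including the use of the VIDAS GFAP&UCH-L1 test for patients with mTBI". Section 7.1 makes it part of the primary endpoint, saying the study will determine that implementation "is not associated with serious side effects during the six-month period of the study". On size, it says: "We expect to test during a six-month period around 1000 patients". The only numerical target there, a lower 95% limit of at least 97.0%, is for the negative predictive value (NPV). Deterioration has no target.

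The summary's outcome measure is "Proportion (%) of neurologic deterioration within 1 week post-TBI", with no split by test result or CT status. Section 3.2 is equally general: "To determine the safety of the new protocol all information regarding the neurological status of the patients in relation to mTBI will be analyzed".

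The event is defined twice:
- Summary, principal outcome: "Deterioration: need for hospital admission or surgery due to TBI in the first week after TBI".
- Section 5.3.1: a GCS fall of more than 2 points without sedatives, a deterioration that warrants intervention, or "Admission to a hospital ward exclusively related to deterioration of neurological condition due to TBI".

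Section 2.1 describes ordinary practice: "Patients with mTBI lesions are often hospitalised in the standard ward".

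**The concern.** The pathway lets a negative test lead to no CT. Test-negative patients managed without CT are therefore the group most directly exposed to the new risk. The stated proportion pools them with test-positive patients, with patients scanned whatever the test shows (GCS 13 or focal deficit, section 5.2), and with test-negative patients scanned at the physician's discretion.

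Two problems follow. Read literally, the summary turns a planned admission for a lesion found on the first CT into a deterioration event, so expected admissions can hide a small number of real harms. Under 5.3.1 those admissions drop out, but a low rate over the whole cohort would still look more precise than the evidence on the unscanned group allows. Section 8.2 expects the results to help policy makers promote the bundle of care, so a safety statement stronger than its evidence would matter.

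**Working it through.** **Inputs from the protocol.** About 1000 patients tested and 10% CT positivity (section 7.1). Patients with lesions are often, not always, admitted (section 2.1).

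**Assumed inputs.** The number of test-negative patients without initial CT is not given; 200 to 500 is used. It must be smaller than the total of test-negatives, because section 5.2 allows CT despite a negative test and requires it for GCS 13 or focal deficit. The share of CT-positive patients admitted is also not given; 50% and 100% are used.

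**Step 1, the plan's own figure.** 1000 × 0.10 = 100 CT-positive patients, as 7.1 states. There is no safety figure to reproduce.

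**Step 2, masking under the summary definition.** Suppose 400 patients are unscanned after a negative test and 1% of them come to harm: 400 × 0.01 = 4 extra events. Exact (Clopper-Pearson) 95% intervals for the whole cohort:

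| CT-positive patients admitted | Without the harm | With 4 harms |
|---|---|---|
| 100 of 100 | 100/1000 = 10.0% (8.2 to 12.0) | 104/1000 = 10.4% (8.6 to 12.5) |
| 50 of 100 | 50/1000 = 5.0% (3.7 to 6.5) | 54/1000 = 5.4% (4.1 to 7.0) |

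In both rows the intervals overlap almost entirely. This step applies only to the summary definition.

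**Step 3, the denominator under 5.3.1.** With zero events the exact two-sided 95% upper limit is 1 − 0.025^(1/n). With x events it is the 0.975 quantile of a Beta(x + 1, n − x) distribution.

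| Denominator | 0 events | 3 events |
|---|---|---|
| 1000 (whole cohort) | 0.37% | 0.87% |
| 500 | 0.74% | 1.74% |
| 300 | 1.22% | 2.89% |
| 200 | 1.83% | 4.32% |

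If the events all occur in the unscanned test-negative group, the whole-cohort limit is 2 to 5 times lower than the limit for that group (1.74/0.87 = 2.0; 1.83/0.37 = 4.9).

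**Step 4, the historical comparison.** The summary compares outcome measures with the preceding six months but sets no margin for deterioration. Assume 1000 patients per period and a 1% base rate. A 1-point rise confined to 200 to 500 patients moves the cohort rate by 0.2 to 0.5 points (0.01 × 200/1000 to 0.01 × 500/1000). The power to detect it at two-sided 5% is about 6% to 17%.

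**The case against.** **The whole-cohort proportion is a legitimate quantity.** This stands. The objective is the safety of a management protocol, and comparing pathway-level deterioration between periods answers that. Risk may also reach beyond the unscanned group, for instance if test-positive patients wait for a result before CT. A reader might infer that the stated measure is simply the wrong one, or that only unscanned test-negative patients bear new risk. The protocol supports neither reading. The measure is incomplete for the claim made, and should be kept.

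**The NPV already covers the exposed group.** Partly true. Section 3.2 counts unscanned patients as CT negative only if they do not deteriorate or need further evaluation leading to CT, so deterioration feeds into the NPV. That bound is loose: it concerns CT findings, mixes scanned and unscanned negatives, and is compatible with up to 3% missed lesions.

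**An analysis plan could add the subgroup.** It could. It would not remove two conflicting outcome definitions from the protocol, or a sample-size statement that promises a safety conclusion without a bound.

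**The narrow definition may be what was meant.** Plausible, since the summary's second objective speaks of unforeseen deterioration. The outcome line beneath it nevertheless counts admission due to TBI without that qualifier.

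**The masking and zero-event figures cannot both describe one measure.** Correct. A background near 10% arises only under the summary definition, and a near-zero count only under 5.3.1. They are alternatives and should not be added together.

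**Conclusion.** The point holds for what the protocol fixes. Section 7.1 claims more than a single unbounded proportion can deliver, and the event has two definitions that would give different counts. Under the summary definition, 1% harm in 400 unscanned test-negative patients would shift the cohort rate by only 0.4 points against a background of perhaps 5% to 10%. Under 5.3.1, zero events would exclude rates above 0.37% in the cohort, but only above 0.74% to 1.83% in the unscanned test-negative group.

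These sizes rest on the assumed 200 to 500 unscanned patients and the assumed admission share. The direction does not: the unscanned test-negative group is only part of the cohort, so its limit is always wider for the same events. A reader might take an assumed specificity times the CT-negative count as the size of this group. That product counts all test-negatives, scanned or not, so the resulting limit would be too favourable to write into 7.1. The 1% neurosurgical figure in section 2.1 has an unclear base and does not serve as a benchmark here.

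**What to change.** 1. Reconcile the deterioration definition in the study summary with section 5.3.1, so that one event definition applies throughout.
2. Keep the pathway-level proportion and its historical comparison. Add, as the key safety measure, the proportion with deterioration among test-negative patients managed without initial CT, with an exact 95% upper limit.
3. In 7.1, replace the statement that the study will determine the absence of an association with an estimate and its achievable upper limit, given as a function of the number of unscanned test-negative patients. For example, with no events: 1.83% for 200, 1.22% for 300, 0.74% for 500. State the expected number as an assumption and say that it is below the total of test-negatives.

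The cost is protocol wording only. Test result, CT status and follow-up contacts are already to be recorded (section 5.3.3). The downside is that the stated safety precision becomes less favourable.

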### 7.2. STATISTICAL ANALYSIS

#### 7.2.1. DATA ANALYSIS RESPONSIBILITY

SERMAS will be responsible for the data analysis for the primary study objective (performance evaluation of the VIDAS TBI assay) in collaboration with BioMérieux. Data analysis for the secondary objectives will be performed by SERMAS.

#### 7.2.2. DATA RETENTION

The site must retain its clinical trial records relating to the trial for at least 3 years after the clinical trial is completed or terminated.

### 7.3. STUDY PARTICIPANT CONFIDENTIALITY

## BRAINII2-IMPLEMENTATION STUDY

Gathering and processing of personal data will be done in keeping with article 9 of European Regulation on data protection 2016/679 (General Data Protection Regulation) and the counsel on data Protection of 27th April 2016. It will follow the Spanish Organic Law on Personal data Protection 3/2018.

To protect the participant's confidentiality, data will be pseudonymised.

## ETHICAL AND REGULATORY CONSIDERATIONS

The study will be conducted in accordance with the Declaration of Helsinki (amended at Fortaleza in 2013; for full version see <http://www.wma.net>), Good Clinical Practice Guidelines (GCP, ICHE6) and all applicable local regulations.

The study will only begin after receiving the approval of the local ethics committee and the waiver of specific informed consent, as the practice will be following standard management of TBI.

The Principal Investigator is responsible for ensuring compliance with these regulations, and adherence to protocols that have been approved by the ethics committee.

## 7.4. STUDY REGISTRATION

This study will be registered in the clinical trials registry: <http://clinicaltrials.gov/> before its beginning.

## 8. SUBJECT RISKS AND BENEFITS

### 8.1. FORESEEABLE RISKS AND THEIR MINIMIZATION

No therapeutic interventions will take place in the context of the implementation studies. Diagnostic interventions include blood sampling, outcome assessments and CT imaging. All of them will be based on activities performed for the actual management of mTBI in the Hospital and accepted and promoted by different medical societies in our country. CT imaging is performed as a standard of care. Blood sampling for biomarker assessment and/or other determinations will be performed depending on clinical indication by the attending physician and related to the accepted protocol for managing mTBI.

### 8.2. POTENTIAL BENEFITS OF PROPOSED RESEARCH

There is no direct benefit for the patients. The results will be directly relevant to society in general and to future patients who suffer mTBI and will help policy makers to promote the mTBI bundle of care devised in our hospital.

## BRAIN12-IMPLEMENTATION STUDY

The results of this study could have a major impact on the management of patients with TBI: 1) By reducing the number of unnecessary CT scans; 2) by improving management of patients being at risk as patients testing positive could be managed in a more urgent way (those patients with more probability of having a lesion in CT); and 3) by a more objective management of patients.

### 8.3. ADVERSE EVENTS

No structured adverse event reporting will be implemented. However, we will capture any serious complication which may occur during the clinical course in the CRF and analysing the clinical records.

## 9. ARCHIVING OF DOCUMENTS AND STUDY DATA

In accordance with Good Clinical Practice the following documents related to this research are to be archived:

By the physician investigators:

- for a period of 15 years following the end of the study

The protocol and any amendments to the protocol

The case report books

The source files of all included participants

All other documents and correspondence relating to the study

All these documents are the responsibility of the investigator during the archiving period.

By the sponsor:

- For a period of 15 years following the end of the study

The protocol and any amendments to the protocol

All other documents and correspondence relating to the study

All these documents are the responsibility of the sponsor during the archiving period.

No displacement or destruction of documents or data can be carried out without the agreement of the sponsor. At the end of the regulatory archiving period, the sponsor will be consulted concerning destruction. All data, documents and reports may be subject to audit or inspection.

## 10. PROTOCOL MODIFICATIONS

A substantial change is a modification likely to have a significant impact on the protection of the study participants, on the validity of the study or its results, on the interpretation of scientific documents that support the study design or conduct. A substantial change is subject to a written amendment submitted to the sponsor.

All amendments are validated by the sponsor, and by all study stakeholders. Prior to its implementation, the sponsor must obtain a favourable opinion from the ethics committee (CPP). All investigators will be informed of any amendment to the study protocol.

## 11. PROVISIONAL STUDY CALENDAR

- Staff training and technology deployment: January\_March 2025
- Start of inclusions: April 2025
- Length of inclusion period: 6 months
- End of inclusions: September 2025
- Length of participation of each subject: 10 days
- Total length of the study: 12 months

## 12. COMMUNICATION AND PUBLICATION RULES

Data analysis will result in a written report that will be submitted by the sponsor, who shall submit it to the ethics committee. Any written or oral communication of research results must receive prior approval of the coordinating investigator and of any committee established for the research. The publication of the main results must indicate in the acknowledgements the name of the sponsor and investigators, methodologists, biostatisticians and data managers who substantially participated in the research, and the name of the funding source. The name of any person contributing to writing or editing the manuscript, if not already in the author list, should also be given in the acknowledgements. Publication will follow international standards of writing and publishing (The Uniform Requirements for Manuscripts of the ICMJE, April 2010) and respect the criteria for authorship.

## 13. PARTNERSHIP

The BRAINI2 study has received financial support from the European Institute of Innovation and Technology (EIT Health) for the business plan 2022-2024. SERMAS (Hospital Universitario 12 de Octubre and FIBH12O Madrid), Grenoble University Hospital (CHUGA) and the University Grenoble Alpes, Institut Catalá de la Salut (Hospital Vall D'Hebron), Hospital of the Technical

BRAINII2-IMPLEMENTATION STUDY

University of Munich (TUM Klinikum), CHU Nantes, CHU-Clermont-Ferrand, Luzerner kantospital, association Daño Cerebral Invisible and BioMérieux are partners to conduct the project.

15. APPENDICES

Appendix 1: mTBI bundle of care.

These documents are available in separate files.
